### **6.3 Subject Population(s) for Analysis**

The data from all subjects will be analyzed without knowledge of whether the data comes from a control or test condition. After breaking the code, data will be grouped accordingly. All data will be analyzed in two different ways. Using a paired t-test data from subjects that have completed the two anesthesia sessions of the study will be analyzed and plotted. Separately, using an unpaired t-test all data will be grouped together including that from subjects who did not finish the trial. In this way the data will be compared. Only data from subjects that failed the toxicology screen will be excluded.

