### **2.2 Duration of Study**

Screening: 1 week

Intervention: 6 weeks total

Follow-up: 2 weeks

Part 1: We will enroll up to 8 test subjects in a full scale trial. The estimated duration of this trial will be approximately 16 weeks followed by a 2 week follow up period.

Week 1: Explanation of the trial and signature of informed consent form. Detailed medical exam and physical exam. Toxicology screen and acceptance into trial. Training with psychomotor tests.

Week 2: Volunteers will be exposed to isoflurane anesthesia as described below and then receive and injection of either a saline solution or caffeine citrate (both investigators and subjects will be blind to composition of injection). Psychomotor tests will be carried out. There will be a toxicology screen. Later that day and then the day after the session, there will be a telephone follow-up with the subject.

Week 3: There will be a telephone follow-up with both volunteers.

Week 4-6: Volunteers will be exposed to isoflurane anesthesia as described below and then receive and injection of either a saline solution or Caffeine (both investigators and subjects will be blind to composition of injection). Psychomotor tests will be carried out. There will be a toxicology screen. Later that day and then the day after the session, there will be a telephone follow-up with the subject.

Weeks 6: There will be telephone follow-ups with both volunteers.

Week 7: There will be a final series of telephone follow-up with both volunteers. If there are no issues identified, this will be the last contact with the volunteers.

We are suggesting that the trial take place over 16 weeks due to scheduling conflicts i.e. the possibility that subjects are not available. We hope to anesthetize 2 subjects per single lab day.

We are asking to be allowed to enroll up to 8 additional volunteers, but we will only require 6-8 to complete the study. If we need additional subjects due to dropout from the trial, we will ask the IRB for additional subjects. After 6 subjects are completed we will submit a continuing review after enrolling 6 additional subjects in order to inform the IRB of the study progress, how subjects tolerated the dosing changes, and if there were any subject safety issues.

If we are given IRB approval, the next set of test subjects will take 4-6 weeks to complete the trial. There will also be a two week follow-up period.

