## 6.2 Statistical Methods

We hope to use a simple paired t-test to analyze the data, using volunteers as their own controls.

Crossover study - Each volunteer receives anesthesia 2 times: once without drug (control) and once with caffeine (test). Our animal studies suggest that variance is dramatically minimized when test subjects can be used as their own controls, in this manner. If humans recapitulate the rodent studies then 8 volunteers should provide an adequately

sized sample to answer the research question. The study was originally divided into two parts. The first part, the Pilot study has been completed.

Part 1: In order to demonstrate feasibility and safety, we carried out a pilot study of 2 healthy human volunteers to assess whether caffeine aids these subjects in recovering from isoflurane anesthesia. Recovery times were measured in three ways: as the time between the time when anesthetic is terminated until the subject starts to gag, can open his eyes, and the subject is able to respond to simple commands (like squeeze the clinician's hand). Each of the three endpoints was monitored and plotted separately. In this pilot study caffeine citrate (caffeine) was used at 10 mg/kg. By comparing subjects that wake from anesthesia who are injected with a saline solution to subjects that are injected with caffeine we were able to show that caffeine is as efficient in humans as in rodents. Now that we have demonstrated safety and feasibility, if the IRB gives us permission, we will continue to Part 2 of our study. Time from the end of anesthesia to eye opening will be analyzed, as will be the time from the end of anesthesia to response to a simple command. Each parameter (gagging, eye opening and response to command) will be analyzed and plotted separately.

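### The all-data unpaired t-test in Section 6.3 ignores that completers appear in both groups, so its standard error is wrong, and neither of the two planned tests is named primary

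*Combined protocol and SAP*

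**What the plan says.** Section 6.3 of the combined protocol and SAP states: "All data will be analyzed in two different ways". The first way is a paired t-test on subjects who had both anesthesia sessions. The second is: "Separately, using an unpaired t-test all data will be grouped together including that from subjects who did not finish the trial". The only exclusion is given as: "Only data from subjects that failed the toxicology screen will be excluded". Each completer therefore enters the second test twice, once in each group. On how the two results relate, the section says only: "In this way the data will be compared".

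The Study Summary names the paired t-test alone. So does Section 6.2, in softer words: "We hope to use a simple paired t-test to analyze the data, using volunteers as their own controls". Section 6.2 also gives the reason for pairing: "Our animal studies suggest that variance is dramatically minimized when test subjects can be used as their own controls, in this manner". Section 9.1 mentions a t-test without saying which kind. No section calls either test primary.

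Non-finishers are expected. Sections 3.13 and 6.2 both anticipate dropout, and Section 2.2 says: "We are asking to be allowed to enroll up to 8 additional volunteers, but we will only require 6-8 to complete the study". On replacement it adds: "If we need additional subjects due to dropout from the trial, we will ask the IRB for additional subjects".

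**The concern.** An unpaired t-test assumes that the two groups contain different, independent subjects. Here most or all subjects are in both groups. The test leaves out the covariance between a subject's two sessions, so its standard error is too large if that covariance is positive and too small if it is negative. The plan relies on positive within-subject correlation to justify a small sample and then discards it in its second test.

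Two things are at stake. The only analysis that uses non-finishers' data misstates its own precision. And with 6 to 8 completers the two tests can return opposite verdicts, with no stated rule for which one the conclusion rests on.

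**Working it through.** **Inputs.** From Section 6.1 (rats): saline mean 540 s, SD s1 = 159.04; caffeine mean 269.67 s, SD s2 = 103.69; difference 270.33 s. The 0.01 level also comes from Section 6.1, where it is only a sample-size criterion. Completers: 6 or 8, from Section 2.2. Assumptions: correlation ρ of 0.3, 0.5 or 0.7 (the documents give none), two-sided tests, normal data. *6+1+1* means 6 completers, one subject with a saline session only and one with a caffeine session only.

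**The plan's own figure.** Pooled SD = √((159.04² + 103.69²)/2) = 134.25. A two-sample t-test at two-sided 0.01 with 95% power needs 11 per condition (power 95.9%; 97.6% at 12). The plan states 12, so the inputs are read as intended.

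**Standard error.** With n pairs and k sessions per arm:

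- Reported by the unpaired test: Var = (s1² + s2²)/k
- True: Var = (s1² + s2²)/k − 2·n·ρ·s1·s2/k²

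Here s1² + s2² = 25,293.7 + 10,751.6 = 36,045.3, and s1·s2 = 16,490.9.

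For 8 completers (n = k = 8) the reported SE is √(36,045.3/8) = 67.12 s. At ρ = 0.5 the true SE is √((36,045.3 − 16,490.9)/8) = 49.44 s, and the ratio is 1.358.

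For 6+1+1 (n = 6, k = 7) the reported SE is √(36,045.3/7) = 71.76 s. At ρ = 0.5 the true SE is √(5,149.3 − 12 × 0.5 × 16,490.9/49) = 55.95 s, and the ratio is 1.283.

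| | ρ = 0.3 | ρ = 0.5 | ρ = 0.7 |
|---|---|---|---|
| True SE, 8 completers (s) | 57.17 | 49.44 | 40.25 |
| Reported/true | 1.174 | 1.358 | 1.668 |
| True SE, 6+1+1 (s) | 62.75 | 55.95 | 48.19 |
| Reported/true | 1.144 | 1.283 | 1.489 |

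The ratio is 1.000 at ρ = 0. At ρ = −0.3 with 8 completers it is 0.886, so the SE is 11% too small.

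**Error rates and disagreement.** Bivariate-normal simulation, 100,000 trials per setting, pooled-variance unpaired t-test, no period effect. Disagreement means that one of the paired and unpaired tests is significant and the other is not, under the full rat effect of 270 s.

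| | ρ = 0.3 | ρ = 0.5 | ρ = 0.7 |
|---|---|---|---|
| Unpaired type I error at nominal 5%, 8 completers | 2.7% | 1.5% | 0.5% |
| Same, 6+1+1 | 3.1% | 1.9% | 0.9% |
| Either test significant at 0.01 under the null, 8 completers | 1.2% | 1.1% | 1.0% |
| Same, 6+1+1 | 1.4% | 1.1% | 1.1% |
| Disagreement at 0.01, 8 completers | 11% | 10% | 10% |
| Same, 6+1+1 | 28% | 22% | 19% |
| Same, 8 completers plus one single session per arm | 12% | 8% | 6% |
| Disagreement at 0.05, 8 completers | 1.8% | 1.3% | 0.8% |
| Same, 6+1+1 | 8.2% | 4.7% | 3.0% |

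The paired test holds about 5% throughout. Disagreement runs both ways: in 6+1+1 at 0.01, only the unpaired test is significant in 23% / 14% / 4% of trials, and only the paired test in 5% / 8% / 14%.

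**How much a correct all-data analysis would change.** Comparator: REML mixed model with random subject, fixed treatment and period, Kenward-Roger degrees of freedom. Its disagreement with the paired test at 0.01 is 9% / 5% / 1% (8 completers) and 21% / 14% / 7% (6+1+1). Correcting the standard error thus removes 2 / 5 / 9 points and 7 / 8 / 12 points of the disagreement. The rest arises because the analyses use different data and degrees of freedom.

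**The case against.** The case for leaving the text alone has real force.

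- **The lead test is clear enough.** The Study Summary and Section 6.2 name only the paired test, and Section 6.3 sits under analysis populations and reads as completers against everyone. This stands in part: the paired test is the implied lead. But Section 6.3 sets the two tests side by side unranked, and nothing says what follows if they differ.
- **The error is conservative.** At the positive correlation that the documents imply, this is so, and no material false-positive inflation is claimed. The standard error is still wrong, and with 8 completers at ρ = 0.7 power at 0.01 is 89% unpaired against 99% paired.
- **The large disagreement figures depend on the setting.** They use 0.01, which is not stated as an analysis level, and two non-finishers who each contribute one session. This stands. At 0.05 the range is 0.8–8.2%, and with a single non-finisher about 1.6–4.0%.
- **The mixed model is no clear gain.** In 6+1+1 its type I error at nominal 5% is about 5.9% / 5.5% / 5.2% (7.1% at ρ = 0). These values are approximate at this size, because the subject variance was estimated as zero in 26% / 14% / 5% of trials and a convention for degrees of freedom is then needed. With random subject only, it also assumes one residual variance, although the rat SDs differ. Its SE gain over the paired test is only 5% / 3% / 1% with variances estimated. All of this stands, and it is why the paired test should stay primary.
- **Rat figures may not transfer to humans.** Section 6.1 says so itself. The direction of the SE error for a given sign of correlation is firm; the sizes are illustrative.

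**Conclusion.** The point holds and is minor. As written, Section 6.3 prescribes a test whose standard error is wrong whenever a completer's two sessions are correlated. It is too large by 14–67% over correlations 0.3–0.7 and the two completion patterns tabulated, and too small if the correlation is negative. The paired analysis is unaffected. What remains is a misstated precision in what should be a supportive analysis, and two tests that can conflict in either direction with no pre-stated rule. The percentages rest on rat SDs, the disagreement figures also on the full rat effect, and all on assumed correlations and an assumed split of non-finishers.

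**What to change.** Before the code is broken:

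1. State in Sections 6.2 and 6.3 that the paired t-test on subjects completing both sessions is the primary analysis and that the conclusion rests on it.
2. Label the all-data analysis supportive. Replace the unpaired t-test with a linear mixed model: random subject, fixed treatment and period, Kenward-Roger degrees of freedom.
3. Say that any disagreement will be reported but not used to choose between the analyses.
4. Make the Study Summary and Sections 6.2, 6.3 and 9.1 name the same test.

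The label resolves the conflict between verdicts. The model addresses the standard error only, and some disagreement will remain. In 6+1+1 at 0.01 and 270 s, power is 72% / 78% / 88% for the mixed model, 58% / 72% / 89% paired and 76% / 78% / 79% unpaired.

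The cost is a few sentences, no extra subjects or data, and a supportive analysis that is mildly anti-conservative instead of conservative.

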## 7. RISKS AND BENEFITS

### 7.1 Risks and Likelihood of Occurrence

#### *Anesthesia risks:*

Overall, anesthesia is extremely safe. Our hospital administers anesthesia thousands time every year with minimal complications directly related to anesthesia. However, there are potential risks for general anesthesia. The likely risks in patients of the general population include, but are not limited to, post anesthesia nausea and vomiting (up to 30%), mild to moderate sore throat, transient hypoxia (low oxygen level), transient blood pressure and heart rate changes (sinus arrhythmia). Most people do not experience any of these events. They are reversible and have no long term consequence.

The more severe risks, but less likely, are awareness, under anesthesia, aspiration pneumonia (up to 0.03% - that is the reason that you are told not to eat and drink for 8 hours prior to the anesthesia so that your stomach can be as empty as possible), severe hypoxia due to aspiration or difficult airway, severe hyper or hypotension, sustained arrhythmia, dental damage, vocal cord damage and reactions to drugs we administrate. These events do not commonly occur in the healthy population. With the screening tests in this study, these events are very unlikely to occur. If they occur, they will be very unlikely to cause long term consequences with proper treatments.

The most severe risks are unexpected difficult airway, including difficult mask ventilation and difficult intubation, and malignant hyperthermia (MH), a genetic associated reaction to anesthesia (0.002-0.005%). These are considered rarely events in Anesthesia although severe consequences, such as organ damage or even death may occur. We will carefully screen the subjects based on our exclusion criteria to minimize these risks. Therefore, these risks will be further reduced in the population of our study because of careful screening carried out prior to the administration of anesthesia. In addition, our anesthesia location and anesthesiologists are well-equipped to handle these situations so that the damage will be as minimal as possible.

Assessing risks for this trial are somewhat complicated. We will be recruiting healthy volunteers for this trial, while most of the available data comes from the pool of people receiving anesthesia for surgery. Most of these surgical patients are quite sick and are therefore susceptible in ways that healthy people are not.

As an example: A common number used in anesthesia related deaths in ~1 per hundred thousand (see Fig. 1 in ref (Haller *et al.*, 2011)). Different recent studies have different numbers. Some studies have higher numbers of deaths (~2 per hundred thousand (Kawashima *et al.*, 2003)) while others have lower number of deaths (~4 per million, (Aitkenhead, 2005)). The problem with these numbers is that they include all anesthesia's including those in sick patients. Sick patients have most of the adverse reactions. I have only found a single study that examined ASA-1 patients by themselves (ASA-1 patients are healthy and are similar to those we hope to enroll). This study, which covered a span of 14 years found zero anesthesia related deaths in this 14 year interval in ASA-1 patients (Khan & Khan, 2011). This is why anesthesia studies in healthy human volunteers have been allowed in the past. There were ~22,000 ASA-1 patients tracked.

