## **2.7 Primary Study Endpoint**

The goal of the study is to determine whether caffeine speeds emergence from anesthesia. The primary endpoint will be a measurement made following termination of anesthesia in the human volunteers. This will be the time between terminating delivery of anesthetic and the subject opening his eyes. This measurement will constitute the "waking" time for each subject.

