#### **3.5 Inclusion Criteria**

1. Age 25-40
2. Male
3. Normal healthy subject without systematic diseases or conditions
4. Metabolic Equivalents of Functional Capacity  $\geq 5$
5. Low risk for Obstructive Sleep Apnea (OSA) based on the screening test (STOP-bang score established by American Society of Sleep Apnea): Yes to > 3 items- high risk of OSA
6. No History of Arrhythmia (Baseline EKG will be obtained during the history and physical session), seizure, liver and kidney diseases
7. BMI < 30 kg/m^2
8. No prior difficulty with anesthesia
9. No personal or family history of malignant hyperthermia
10. No history of any mental illness
11. No history of drugs or alcohol abuse (urine drug screens required).
12. Subjects capable of giving consent.
13. Living less than 30 miles away from UC.
14. No history of seizure disorders.

15. No history of head trauma.

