oximetry, BIS monitor and temperature, will be used to assess the subject (see below for further details). The subject will then be asked to breathe 100% O2 via a facemask for two minutes. After the lungs are filled with 100% O2, the subject will be given propofol (2mg/kg), as an IV bolus, to induce anesthesia. Within 1-2 minutes, the subject will become unconscious. If the subject is still conscious, an extra dose of propofol (0.5 to 1 mg/kg) will be given until the subject is in a deeper stage of anesthesia. A Laryngeal Mask Airway (LMA), a rubber airway device, will be inserted via the mouth into the larynx. This device will help to optimize the patency of the airway while the subject is completely anesthetized. This allows the subject to breathe easier without the help of a ventilator. This is the induction phase of anesthesia. After induction, the subject will be given isoflurane (1.0 MAC, as adjusted by age and weight by the anesthesia machine) for 60 minutes. This period is called the maintenance phase of anesthesia. 60 minutes will ensure that each subject reaches anesthetic equilibrium. Oxygen flow will be kept at 2 L/min during the maintenance phase. Ten minutes before terminating the isoflurane, volunteers will be infused with a solution containing saline (control) or with caffeine (test). After the termination of isoflurane, the subject will be allowed to wake up. This phase is called the emergence phase of anesthesia. During the emergence phase, Oxygen flow will go up to 8 L/min to avoid rebreathing. We will test whether the caffeine shortens the emergence phase of anesthesia.

[EKG, respiratory rate, end tidal CO2, pulse oximetry and temperature are monitored continuously, once the volunteer is connected to the monitoring machines. A bispectral index (BIS) monitor, will continuously measure depth of anesthesia. Prior to starting the procedure, blood pressure will be measured every 5 minutes; this measurement of blood pressure will provide the baseline for subsequent BP measurements. Blood pressure will be measured every 2 minutes during the first 10 min of the anesthesia, which includes the induction period. BP will be measured every 5 min throughout the course of anesthesia and the first 30 min in the PACU. After that, BP will be measured every 10 min until the subject is discharged. This data is stored automatically for each patient in our hospital's Epic database].

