We are using human volunteers twice, not four times like the rat population, we expect higher variance. Nonetheless, we expect 8 total volunteers will satisfy our study. This is because we are using a higher concentration of caffeine (7.5 mg/kg), which should produce a larger response than the 5 mg/kg shown above, and we will employ a lower concentration of isoflurane (1 MAC), which should be easier to antagonize.

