#### ***Risks of Caffeine:***

Caffeine is very safe and commonly used in the household and also used clinically in certain conditions, such as post-dural puncture headache in post-partum women and sleep apnea in premature infants. The doses used in this study are lower than those used in infants for sleep apnea. The FDA categorizes caffeine as "Generally Recognized as Safe". However, caffeine can have side effects, such as palpitation, seizure, sleepless or nervousness. Seizures are exceptionally rare and occur at much higher concentrations than will be used in the current study. We don't expect caffeine's effects to be any different with or without anesthesia. Two clinical trials, one in adults and another in children, showed that it was safe to administer caffeine to anesthetized patients (Khalil *et al.*, 2008; Steinbrook *et al.*). Both these trials used caffeine and sodium benzoate.

In this protocol we describe a procedure where anesthetized healthy human volunteers would be given 15 mg/ kg caffeine citrate, 10 minutes before terminating anesthesia. The caffeine is to be administered slowly across a 10-minute time window so as to prevent a large spike in circulating caffeine levels. We propose using healthy, low body mass male volunteers exclusively in this trial. In these low body mass, low weight volunteers 15 mg/ kg caffeine and citrate will translate to 750-1200 mg caffeine citrate in total. Normalizing for the weight of the volunteers represents a more rigorous pharmacological approach than simply giving everyone the same amount of caffeine citrate. Note that 15 mg/ kg caffeine citrate is equivalent to ~7.5 mg/ kg of caffeine base. Thus 750-1200 mg caffeine citrate corresponds to 375-600 mg of pure caffeine.

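### Section 7.1 rests the low awareness risk partly on screening, which does not address awareness caused by infusing an intended isoflurane antagonist while isoflurane is on, and no recall question or BIS comparison covers that window

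*Combined protocol and SAP*

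**What the plan says.** Section 7.1, under Anesthesia risks, opens its second tier of risks with "The more severe risks, but less likely, are awareness, under anesthesia, aspiration pneumonia" and continues through hypoxia, blood pressure extremes, arrhythmia, dental and vocal cord damage and drug reactions. It gives two reasons for expecting few of these: they are uncommon in healthy people, and "With the screening tests in this study, these events are very unlikely to occur". No rate is given for awareness.

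The study drug is started "10 minutes before terminating anesthesia" (Section 7.1, Risks of Caffeine) and is infused by pump over 10 minutes (Section 4.2A). Section 6.1 justifies the sample size partly by the use of a "lower concentration of isoflurane (1 MAC), which should be easier to antagonize".

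The primary endpoint in Section 2.7 has its clock start at isoflurane off: "This will be the time between terminating delivery of anesthetic and the subject opening his eyes". The Study Summary names the gag reflex as the primary measure instead, but from the same starting point. So do the response to command in Section 2.8 and the measures listed in Section 5.2.

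On monitoring, Section 5.2 states: "A bispectral index (BIS) monitor, will continuously measure depth of anesthesia". It also keeps at least two anesthesiologists present during anesthesia. Follow-up calls the same day, the next day and a week later (Sections 2.9 and 5.2) check recovery and adverse events in general terms.

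**The concern.** Of the anesthesia risks listed in Section 7.1, awareness is the one most directly tied to what the drug is meant to do. The hypothesis is that caffeine reverses anesthesia, and it is given while isoflurane is still being delivered and a laryngeal mask is in place. Screening selects healthy volunteers; it says nothing about a risk created by the intervention itself. The Risks of Caffeine text covers palpitation, seizure, sleeplessness and nervousness, and expects caffeine to act alike with or without anesthesia. It does not consider that lightening anesthesia might be part of the intended effect.

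At stake are an accurate risk statement for healthy volunteers who gain little or nothing personally, and the trial's ability to say anything about awareness at the end. If nobody asks about recall and the depth trace is not compared between sessions, a report of no awareness would rest on spontaneous mention alone.

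**Working it through.** The plan states no awareness rate, so there is no figure to reproduce. The check sets the text side by side, with a short calculation for scale.

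**1. Does screening address the risk?** Sections 2.3, 3.5 and 5.1 give the content: history, physical examination, EKG, urine toxicology, sleep apnea score, functional capacity, BMI and similar criteria. The nearest item is "No prior difficulty with anesthesia". That bears indirectly on a volunteer's own susceptibility, but not on awareness induced by caffeine.

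**2. Timeline, with isoflurane off as time 0.**
- Isoflurane maintenance: −60 to 0 min (Section 5.2).
- Study-drug infusion: −10 to 0 min (Sections 4.2A and 5.2).
- All defined emergence times: from 0 onward (Sections 2.7, 2.8 and 5.2).
- Overlap of the infusion with any defined outcome window: 0 min.
- Overlap of the infusion with continuous BIS: the full 10 min.

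The window is therefore observed but not captured as an outcome. No BIS threshold, summary or comparison is defined. Section 8.7 names seizure, arrhythmia and a blood pressure fall as events to report, but not awareness or arousal. No recall question appears in the schema, the cognitive tests, the calls or the safety plan. The 20-word list in Section 5.2 tests memory after waking, not recall of the anesthetic.

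**3. Does earlier work settle it?** Section 6.1 says that neither 7.5 mg/kg caffeine nor isoflurane at 1 MAC was studied in rats. The rat data used for sizing are at about 1.5 MAC and 5 mg/kg. The pilot was two volunteers at 10 mg/kg caffeine citrate (Sections 1.2 and 6.2); this trial uses 15 mg/kg.

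**4. What could the trial show?** The plan requires 6 to 8 completers (Section 2.2), each with one caffeine session. The chance of at least one event in 8 sessions is 1 − (1 − p)^8. With p assumed, because the documents give none:

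| Assumed risk per caffeine session | Chance of at least one in 8 |
|---|---|
| 0.1% | 0.8% |
| 1% | 7.7% |
| 5% | 33.7% |
| 10% | 57.0% |

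With zero events, the one-sided 95% upper bound is 1 − 0.05^(1/n): 31.2% for n = 8 and 39.3% for n = 6.

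**5. Signed times and the paired difference.** Let c and s be a subject's event times from isoflurane off in the caffeine and saline sessions. On a clock started at the infusion, they are c + 10 and s + 10. The difference is (c + 10) − (s + 10) = c − s. A negative value for an early event thus gives the same paired difference as timing from infusion start, provided the infusion starts 10 minutes before isoflurane off in both sessions. If no early event occurs, nothing changes.

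**The case against.** A reader might infer three stronger claims. The documents support none of them.

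**That the window is unobserved.** BIS, EKG, respiratory rate and end-tidal CO2 run continuously, and at least two anesthesiologists are present. No muscle relaxant is planned, so movement would be visible. Section 14 also commits to publishing vital signs with and without caffeine, although it does not name BIS.

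**That early arousal would be scored zero or dropped, biasing the primary endpoint.** No section sets such a value to zero, and Section 6.3 excludes only data from subjects who fail the toxicology screen. A negative time is available under the plan as written; the plan is merely silent. If someone did force a zero, the mean caffeine benefit would be understated, not created.

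**That the plan predicts arousal under isoflurane, or that safety monitoring would miss it.** The Section 6.1 remark about antagonism supports a smaller sample for waking times; it does not forecast waking at 1 MAC. The adverse event definition in Section 8.2 is broad, every session is reviewed, and a volunteer who mentioned recall would be recorded.

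There is also reassuring evidence. Rats given 25 mg/kg under isoflurane showed no significant change in vital signs 10 minutes later (Section 1.1.3). The adult trial described in Section 7.1 gave 500 mg to 65 anesthetized patients 15 minutes before emergence without adverse effect. The two-person pilot used the same 10-minute infusion.

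All of this stands, and it limits the point. It does not answer the narrower one. The rat work was not done at 1 MAC, the pilot used a lower dose, and the protocol's account of the adult trial does not say that recall was asked about. Rarity in healthy people is a separate reason in Section 7.1, but it too concerns anesthesia without this drug.

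**Conclusion.** The point holds as a gap in the risk description and in data capture. Section 7.1 relies partly on screening for a risk that screening does not address, and the plan neither asks about recall nor uses the depth trace for the 10 minutes in which the drug and isoflurane overlap.

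Its size cannot be stated as a bias or an event rate: the frequency of early arousal is unknown and may be very low. What can be said is that a clean result in 6 to 8 caffeine sessions would exclude only risks above roughly 31% to 39%, and then only if awareness is actively sought. The table above rests on assumed risks and independent sessions.

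The consent form and some pages were not in the copy available, so absence is claimed only for the remaining text. The change is worth making because it is nearly free and improves detection of a safety event, not because the primary analysis is shown to be wrong.

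**What to change.** 1. **Section 7.1.** Stop attributing the low risk of awareness to screening, and state in the anesthesia or caffeine risk text that caffeine given while isoflurane is on could in principle raise it.
2. **Sections 2.9 and 5.2.** Add one recall question, in fixed wording, to the same-day and next-day contacts after both sessions. Section 2.9 allows email or text in place of a call, so the wording should be the same in each form. Asking while both sessions are still blinded keeps the comparison fair.
3. **Section 6.2.** Summarise BIS over the 10-minute infusion, caffeine against saline, within subject and descriptively. Section 5.2 says monitoring data are stored automatically, but that sentence directly follows the blood pressure text, so confirm that the BIS trace is included.
4. **Sections 2.7 and 5.2 (minor).** State that any gag, movement or eye opening during the infusion is recorded with a negative time relative to isoflurane off.

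The cost is protocol wording, one extra question for the volunteer and one extra table. Dose, timing and care are unchanged.
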